4.1 Inclusion criteria

Subjects must fulfill **all** of the following criteria at screening to be eligible for the study. The screening period is defined as that interval that begins at the time the informed consent is signed and ends with the qualification of the subject for entry into the study (i.e. when subject has met all eligibility criteria):

1. Able to provide written informed consent before any study-specific assessment is performed. The AHF diagnostic assessments performed as per current local institution/hospital standard practice or as part of routine clinical care can be used to support patient screening even if performed before obtaining informed consent.
2. Male or female \geq 18 years of age with body weight \geq 40 Kg and \leq 160 Kg.
3. Systolic blood pressure \geq 125 mmHg at the beginning of the screening period (after ICF signature) and at the end of the screening period (prior to randomization).
4. Admitted/hospitalized for AHF. AHF is defined as including all of the following measured at any time between presentation and the end of screening:
 - a. Persistent dyspnea at rest or with minimal exertion, at screening and at the time of randomization, despite standard background therapy for acute decompensated heart failure including intravenous furosemide of at least 40 mg total (or equivalent)
 - b. Pulmonary congestion assessed through physical examination and chest X-Ray obtained during routine clinical practice at any time between presentation and the end of screening (prior to randomization)
 - c. N-terminal pro B-type natriuretic peptide (NT-proBNP) \geq 2,000 pg/mL or BNP \geq 500 pg/mL. For patients treated with valsartan/sacubitril (Entresto®), BNP is not suitable and only NT-pro-BNP should be assessed
5. Able to be randomized **within 16 hours** from presentation to the hospital [presentation starts as the earliest of (1) time of presentation at either the ER/ED, ICU/CCU or ward; or (2) time of first IV loop diuretic for treatment of the current AHF episode prior to arrival at the hospital] *(this includes outpatient clinic, ambulance, or previous hospital including emergency department).*

6. Received intravenous furosemide of at least 40 mg (or equivalent) at any time between presentation and the start of screening for the study

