Patients who discontinued prematurely the study drug are defined as subjects with at least one dose infusion recorded on the “Dosage administration record” eCRF page and “Subject Status” on the eCRF page “Treatment Completion” different from ‘Completed’.

Concomitant treatments

Concomitant medications are collected in dedicated eCRF sections at screening, baseline, 24h, 48h, Day 3, Day 4, Day 5, Day 14, Day 30 and discharge visit; in general, medications taken within the screening period are collected at Screening; medications taken since the initial presentation of the Index Heart Failure event are reported at baseline; medications taken within the 24 hours preceding the visit are entered in eCRF at each post baseline assessment.

Concomitant medications usage will be described by treatment group according to the following details. Medications will be coded using the WHO NOVDD_14_3 dictionary and subsequent versions. As a patient may have taken more than one medication, the total number of medications could be greater than the total number of patients. Continuous variables will be summarized with standard summary statistics, categorical variables with the number and percentage of patients. Percentages will be computed using patients included in the analysis population as denominators.

All medications reported in the eCRF pages corresponding to the day of discharge will be considered as administered during the index hospitalization.

Concomitant treatment administration details will be summarized by treatment group for the FAS and the Safety set.

The analysis will include the following variables:

- Any IV nitrates at the time of randomization (yes/no). A complete description will be provided also by medication, with number and percentage of patients taking at least one dose of medication (obtained from start date and time and non-missing dose recorded at screening on the “Index heart failure hospitalization” eCRF page).

Statistical Analysis Plan

Sponsor: NOVARTIS

Protocol number: CRLX030A3301

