- Any IV loop diuretic medication taken since the initial presentation of heart failure (recorded as “Any medication to report?” in the “IV loop diuretic medication for heart failure” dedicated eCRF page from baseline visit) (yes/no). A complete description will be provided also by Preferred Term for other medication names not listed in the eCRF, with number and percentage of patients taking at least one dose of medication. Moreover, the total dose of IV loop diuretic administered during the index hospitalization (at most for 5 days of hospitalization) will be described. Doses will be converted to Furosemide equivalents for the analysis (Furosemide 40 mg is equivalent to Torasemide/Torsemide 20 mg, or Bumetanide 2 mg, or Etacrynic acid/Ethacrynic acid 50 mg, see Table 5.1-2 below for the conversion factors). The total dose of IV loop diuretic administered during the index hospitalization will be compared between treatment groups using a t-test. For subjects who die before Day 5, the minimum of 2 times of the last recorded dose and 160 mg will be assumed for every day from the date of death up to and including Day 5. Data will be presented overall and by day from randomization. Data after the index hospitalization will be presented separately.

Table 5.1-2: Conversion factor for diuretic medications

Original Unit	Preferred Unit	Multiplication Factor
Furosemide (mg)	Furosemide (mg)	1
Torasemide (mg)	Furosemide (mg)	2
Bumetanide (mg)	Furosemide (mg)	20
Etacrynic acid (mg)	Furosemide (mg)	0.8

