- Any oral (PO) loop diuretic medication taken since the initial presentation (recorded with “PO loop diuretics” ticked on the “Other non-IV medications” dedicated eCRF page from baseline visit) (yes/no). A complete description will be provided also by preferred term for the other name of medication, with number and percentage of patients taking at least one dose of medication. Moreover, the total dose of oral loop diuretic administered during the index hospitalization (at most for 5 days of hospitalization) will be described. Doses will be converted to Furosemide equivalents for the analysis (see Table 5.1-2). The total dose of PO loop diuretic administered during the index hospitalization will be compared between treatment groups using a t-test. For subjects who die before Day 5, the minimum of 2 times of the last recorded dose and 160 mg will be assumed for every day from the date of death up to and including Day 5. Data will be presented overall and by day from randomization. Data after the index hospitalization will be presented separately.
- All non-IV medications taken since the initial presentation (recorded on the “Other non-IV medications” dedicated eCRF page from baseline visit), excluding Per Oral (PO) loop diuretics, will be summarized by medication classification and name of medication, presenting number and percentage of patients taking at least one dose of medication. Data will be presented overall during index hospitalization and by day from randomization. Data after the index hospitalization will be presented separately.

	Statistical Analysis Plan
	Sponsor: NOVARTIS Protocol number: CRLX030A3301

- All IV medications other than loop diuretics taken since the initial presentation (recorded in the dedicated eCRF page from baseline visit) and by day from randomization will be summarized by medication classification and name of medication, presenting number and percentage of patients taking at least one dose of medication. Data will be presented overall during index hospitalization. Data after the index hospitalization will be presented separately.
- All other non-IV prior medication taken 30 days before screening (recorded in the “Other non-IV prior medication” dedicated eCRF page at screening visit) will be summarized by name of medication, presenting number and percentage of patients taking at least one dose of medication.

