Renal deterioration will be assessed as the proportion of patients with an increase of ≥ 0.3 mg/dL from screening in serum creatinine levels. Absolute frequencies and proportions of patients with renal deterioration at each assessment time point in each treatment group will be provided, together with standard errors, asymptotic (Wald) and exact (Clopper-Pearson) confidence limits. Rate of renal deterioration in the two groups will be compared by means of Chi square test at each assessment time point. In case of cell frequencies less than 5, Fisher's Exact test will be used.

Index length of hospital stay

Index length of hospital stay (in hours) will be defined as the index hospitalization discharge date and time (obtained from the "Index hospitalization summary" eCRF page) minus the index hospitalization admission date and time plus 1 minute (obtained from the "hospitalization" eCRF page); it will be presented as elapsed hours.

Subjects still in the hospital at Day 30 will be censored at Day 30. Subjects who die during the initial hospitalization will be assigned the maximum length of stay (including those censored at Day 30) plus 24 hours.

Treatment groups will be compared using a Wilcoxon rank-sum test. Descriptive statistics by treatment group will be presented. Analysis will be done overall and by location for patients presented to Outpatient clinic or office / Ambulance or Emergency Medical Service / Emergency Department / Intensive Care Unit / Coronary or Cardiac Care Unit / Cardiology Ward / General Ward / Other, as recorded on the "Index heart failure hospitalization" eCRF page.

Statistical Analysis Plan

Sponsor: NOVARTIS

Protocol number: CRLX030A3301

Estimated duration (days) of stay in acute care unit (Coronary or cardiac critical care unit / General intensive care unit / Step down unit or telemetry unit / Cardiology department or cardiac ward / General ward), as recorded on the “Index hospitalization summary” eCRF page, will be summarized by treatment group.

Death through Day 30

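### The post-death fill for loop-diuretic dose falls below the last observed dose when that exceeded 160 mg, and the compared total is not started at randomization

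*SAP*

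**What the plan says.** Protocol 9.3.2 prespecifies the comparison: total IV and total oral loop-diuretic dose over the index hospitalization, in furosemide equivalents, compared by t-test. It has no rule for deaths and no five-day limit.

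SAP 5.1 (Concomitant treatments) adds both. The limit is that "the total dose of IV loop diuretic administered during the index hospitalization (at most for 5 days of hospitalization) will be described". The death rule reads: "For subjects who die before Day 5, the minimum of 2 times of the last recorded dose and 160 mg will be assumed". The fill covers each day from death through Day 5. The rule is repeated for oral drug, where "The total dose of PO loop diuretic administered during the index hospitalization will be compared between treatment groups using a t-test". The SAP gives no reason for the 160 mg cap. It does not say whether the last recorded dose is one administration or a day's total.

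On data collection, SAP 5.1 states that "medications taken since the initial presentation of the Index Heart Failure event are reported at baseline". The IV bullet opens with a yes/no item, "Any IV loop diuretic medication taken since the initial presentation of heart failure", and then moves to the total. No sentence starts the compared total at randomization; only the by-day display is counted from there. Criterion 6 of Protocol 4.1 requires that every patient has "Received intravenous furosemide of at least 40 mg (or equivalent) at any time between presentation and the start of screening".

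**The concern.** There are two separate weaknesses.

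First, doubling the last dose suggests that a death should count as greater need. Taking the smaller of that figure and 160 mg works the other way for patients on high doses: their total ends up below that of a survivor who stayed on the same dose. Applying the rule to oral drug is also hard to interpret, because a higher oral dose can reflect a switch from IV treatment rather than greater need.

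Second, a between-arm comparison should rest on what happens after assignment. Doses given earlier cannot respond to treatment. Counting them makes any difference smaller relative to the total and adds variation to the test.

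Intensified IV diuretic is one way a patient can meet the worsening-heart-failure definition, so readers will look at this comparison beside the open-label primary result. The comparison does not itself feed the adjudicated endpoint.

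**Working it through.** **Check of the plan's own figures.** SAP 5.1 equates 40 mg furosemide with 20 mg torasemide, 2 mg bumetanide or 50 mg etacrynic acid. The factors are 40/20 = 2, 40/2 = 20 and 40/50 = 0.8, as in Table 5.1-2.

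**Imputed daily dose.** With D the last daily dose in mg furosemide equivalents, the rule is f(D) = min(2D, 160). The cap binds once 2D > 160, that is D > 80. The result is below D only when D > 160.

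| D (mg/day) | f(D) | Change from D |
|---|---|---|
| 40 | 80 | +100% |
| 80 | 160 | +100% |
| 120 | 160 | +33% |
| 160 | 160 | 0 |
| 200 | 160 | −20% |
| 240 | 160 | −33% |
| 400 | 160 | −60% |

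**Total for Days 1–5, death on Day 2.** The fill covers 5 − 2 + 1 = 4 days.
- D = 240: 240 + 4 × 160 = 880 mg, against 5 × 240 = 1,200 mg for a survivor on an unchanged dose.
- D = 400: 400 + 4 × 160 = 1,040 mg, against 5 × 400 = 2,000 mg.
- D = 80: 80 + 4 × 160 = 720 mg, against 400 mg. Here the rule raises the total.

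**Effect on an arm mean.** The documents give neither mortality before Day 5 nor the doses of patients who die, so both are assumed. Take a proportion p dying, all on 240 mg and all on Day 2. The shift against carrying the last dose forward is p × 4 × (160 − 240) = −320p mg: 1.6, 3.2, 6.4 and 9.6 mg lower at p = 0.5%, 1%, 2% and 3%. Equal p and equal doses in both arms leave the difference between arms unchanged; 1% against 2% would move it by 6.4 − 3.2 = 3.2 mg. With 3,183 patients, 1–2% is about 32–64 deaths in all, and only those last on more than 160 mg are lowered.

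**Pre-randomization dose.** If the 40 mg minimum were all given in hospital and the post-randomization total were T (assumed), its share would be 40/(40 + T): 29%, 17% and 12% for T = 100, 200 and 300 mg. A uniform 40 mg adds no variance; only variation in the earlier dose does. If that dose has standard deviation r times that of the post-randomization total and is independent of it, the standard deviation grows by √(1 + r²): 1.02 at r = 0.2, 1.08 at r = 0.4. The documents give no value for r.

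**The case against.** The other side has good points, and most of them limit the size of the issue.

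- **A reader might infer that the rule generally rewards death.** It does not. For any last dose above 0 and below 160 mg it raises the daily dose. The aim of penalising death is itself an inference, and a cap could be a deliberate guard against extreme values in a t-test. What stands is that a cap set below an observed dose is not explained.
- **A reader might infer that at least 40 mg of earlier drug enters for nearly all 3,183 patients.** The text does not establish this. Protocol 5.5.7 lets the qualifying dose include drug given in an ambulance. The phrase about medication since presentation belongs to a yes/no item, and the screening diuretic is also recorded on another eCRF page. Still, the total is defined over the index hospitalization, the baseline record reaches back to presentation, and nothing removes earlier doses.
- **A reader might infer bias.** Randomization balances earlier doses in expectation, so the cost is noise and dilution.
- **A bolus reading of the last dose, a zero last dose, or double-counting on the day of death** are gaps in detail, not stated errors. An amount assigned per day most naturally means a daily total that stands in for that day's record. Eligible patients should have some IV dose on record. For oral drug with no record, the rule gives no value.
- **Replacing the t-test by worst-rank scoring** would depart from Protocol 9.3.2 and turn a drug-use comparison into a composite of death and dose. That objection stands.

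**Conclusion.** Two stated rules need repair, and the effect is small. The death rule assigns less than the last observed dose only when that dose exceeded 160 mg furosemide equivalents. In-hospital doses given before randomization enter the compared total on the plain reading, though the SAP does not say so outright.

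The arm-mean shift of about 3–6 mg rests on assumed mortality of 1–2%, every death on Day 2, and every such patient on 240 mg. With a mix of doses, fewer patients would be lowered and some would be raised. The comparison is outside the listed objectives and efficacy parameters, so nothing here touches the primary result.

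**What to change.** Amend SAP 5.1 before database lock:

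1. Start the compared total at randomization and end it at 120 hours (Day 5). Tabulate the pre-randomization dose separately as a baseline variable.
2. Define D as the last observed daily total and impute max(D, min(2D, 160)) mg per day. This leaves 40→80, 80→160 and 160→160 unchanged and gives 240→240 and 400→400. State that the imputed amount replaces the recorded dose on the date of death and is not added to it.
3. Keep the t-test.
4. Show the oral total without post-death imputation as a sensitivity summary.

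A rank-sum test with deaths ranked worst is optional as a sensitivity analysis. SAP 5.2 has a precedent for length of stay: "Subjects who die during the initial hospitalization will be assigned the maximum length of stay" plus 24 hours. It need not replace the t-test.

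The cost is minor SAP wording and programming, plus a short clarification of the time window against Protocol 9.3.2. The change concerns an analysis rule only and has no bearing on how patients are treated.

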5.2. EFFICACY DATA

The primary analysis and the analyses of all secondary and exploratory efficacy variables will be based on the FAS. In addition to the primary analysis, the primary efficacy variable will also be analysed using the same primary analysis model on the PP set as supportive information.

Primary efficacy parameter

Worsening Heart Failure/all cause death through Day 5

The primary efficacy variable of the study is the time to in-hospital Worsening of Heart Failure (WHF) requiring rescue therapy or all cause death through Day 5 post randomization.

In-hospital worsening of heart failure (WHF) through Day 5 post randomization includes worsening signs and/or symptoms of heart failure that require an intensification of intravenous therapy for heart failure or mechanical ventilation, renal or circulatory support. Such treatment can include the institution or up-titration of IV furosemide, IV nitrates or any other IV medication for heart failure, or institution of mechanical support such as assisted (invasive or non-invasive) ventilation, ultrafiltration, hemodialysis, intra-aortic balloon pump or ventricular assist device, etc. This endpoint also includes patients who die in this 5-day period of any cause before experiencing episode(s) of WHF.

Time to in-hospital WHF/all cause death through Day 5 post randomization will be analysed using survival analysis.

The time to in-hospital WHF/all cause death will be computed as the number of hours from randomization to the earlier of the onset of in-hospital WHF or death plus 1 minute. The onset of in-hospital worsening heart failure through Day 5 will be the start date/time of event

Statistical Analysis Plan

Sponsor: NOVARTIS

Protocol number: CRLX030A3301

reported at the first assessment point at which the investigator reported worsening heart failure; if death occurred, date and time are reported in the dedicated eCRF section. Subjects without an event will be censored at the earlier of the last post-baseline assessment date or 120 hours after randomization. Subjects without any information after baseline (i.e., randomization) will be considered censored at 1 minute.

In case of missing time of in-hospital WHF or death then 00:00 will be imputed.

Only adjudicated endpoints will be counted in the primary analysis. The “adjudicated endpoint” refers to an endpoint and date of the endpoint that has been confirmed by an independent adjudication committee who has no access to the treatment code. According to the information from the endpoint adjudication committee, the following rules will be applied to determine if an event reported in eCRF should be considered valid for the analysis or not:

Table 5.2-1: Rule for inclusion of events into the analysis

Included in the analysis	
WHF/death reported in the dedicated page of the eCRF and confirmed by adjudication committee	YES
WHF/death reported in the dedicated page of the eCRF and NOT confirmed by adjudication committee	NO

If more than one in-hospital WHF occurred, the first one will be used as the event. Censoring and time will be defined according to the following rule:

Table 5.2-2: Censoring and time rules

	Status	Time
At least one in hospital WHF and/or death occurred and:		
Difference between date and time of first occurrence of WHF/death and date and time of randomization +1 minute >120 hours	Censored	120h
Difference between date and time of first occurrence of WHF/death and date and time of randomization +1 minute \leq 120 hours	Event	Calculated difference
No in hospital WHF and death occurred and:		
Difference between date and time of last assessment* and date and time of randomization +1 minute >120 hours	Censored	120h
Difference between date and time of last assessment* and date and time of randomization +1 minute \leq 120 hours	Censored	Calculated difference

* Last assessment is the date and time of last available post-baseline physician assessment of in-hospital WHF

In case a patient is lost to follow-up, events occurring prior to the time of lost to follow-up will be counted. If no event occurred, then the patient will be censored at the time of last post-baseline in-hospital WHF assessment available.

The primary statistical hypothesis is:

	Statistical Analysis Plan
	Sponsor: NOVARTIS Protocol number: CRLX030A3301

$H_0: \lambda_2/\lambda_1 \geq 1$, i.e., the rate of primary event of in-hospital WHF or all cause death is greater or equal in the serelaxin group relative to the standard of care group versus the one-sided alternative $H_A: \lambda_2/\lambda_1 < 1$, i.e., the rate of in-hospital WHF or all cause death is smaller in the serelaxin group relative to the standard of care group, where λ_1 and λ_2 are the hazard rates for in-hospital WHF or all cause death in the standard of care group and serelaxin group, respectively. The ratio λ_2/λ_1 is the hazard ratio of serelaxin to standard of care.

The hypothesis will be tested based on the FAS with a Gehan's generalized Wilcoxon test at a significance level of 0.025 (one-sided).

The Kaplan-Meier estimates of the survival functions for each treatment group will be plotted and Kaplan-Meier estimates for selected time points with 95% confidence intervals will be tabulated.

The hazard ratio (relative risk) and its associated two-sided 95% confidence interval will be estimated based on a Cox proportional hazards model with treatment assignment as a factor.

In addition, a description of all in-hospital WHF that occurred through Day 5 will be provided: absolute frequencies and proportions of patients with in-hospital WHF at each assessment time point will be presented overall and by concomitant medication (IV therapy with vasoactives, IV therapy with loop diuretics, oral therapy with loop diuretics, IV therapy with inotropes vasoactives) given (new, restarted or increased dose of medication), and/or by the need of mechanical/surgical intervention (yes/no) for the in-hospital WHF.

In addition to the primary analysis, the primary efficacy variable will also be analysed using the same primary analysis model on the PP set as supportive information.

Subgroup (age [65 and 75 cut off], gender, race [Caucasian and other race], region [Western Europe and Eastern Europe], ejection fractions [40% and 50% cut off], prior history of HF [naïve vs. prior history of HF]) analyses will be performed for the primary endpoint.

[figure not shown]
A Cox proportional hazards model will be fitted considering treatment as a factor and covariates the above mentioned subgroup variables. The hazard ratio (relative risk) and its associated two-sided 95% confidence interval will be estimated for treatment and factors/covariates.

An additional supportive analysis of the primary efficacy variable will be performed using all WHF/all cause deaths through Day 5 post randomisation as reported by the investigators, regardless of confirmation from the endpoint adjudication committee.

The time to WHF/all cause deaths through Day 5 post randomisation will be as described for the primary analysis.

	Statistical Analysis Plan
	Sponsor: NOVARTIS
	Protocol number: CRLX030A3301

The Kaplan-Meier estimates of the survival functions for each treatment group will be plotted. Kaplan-Meier estimates at selected time points and their 95% confidence intervals will be provided.

Handling of missing values/censoring/discontinuations

In the analysis of time to in-hospital WHF/all-cause death through Day 5, patients without any event will be censored at the earlier of the last post-baseline physician assessment of in-hospital WHF or 120 hours post randomization.

Subjects without any information after baseline (i.e., randomization) will be considered censored at 1 minute.

In case of missing time of in-hospital WHF or death then 00:00 will be imputed.

Secondary efficacy parameters

The additional efficacy endpoints will be analysed in the FAS. Standard descriptive statistics will be presented for each treatment group at each time point that the endpoint was measured. Two-sided p-values <0.05 will be considered statistically significant; no adjustment for multiple comparisons will be adopted.

Time to in-hospital WHF/All cause death/readmission for heart failure through Day 14 post randomization

Time to in-hospital WHF/all cause death/readmission for heart failure through Day 14 post randomization will be analyzed using survival analysis.

The time to in-hospital WHF/all cause death/readmission will be computed as the number of hours from randomization to the earlier of the onset of in-hospital WHF or death or readmission for heart failure plus 1 minute. The onset of in-hospital WHF through Day 14 will be the start date/time of event reported at the first assessment point at which the investigator reported worsening heart failure (either during the initial hospitalization or re-hospitalization for heart failure); if death occurred, date and time are reported in the dedicated eCRF section "Death – (Endpoint to be adjudicated)"; the date and time of admission of first re-hospitalization with Primary reason for Hospitalization equal to "Heart Failure" will be considered as the readmission moment (as reported in the dedicated eCRF section "Rehospitalization Information (Endpoint not to be adjudicated)"). Subjects without an event will be censored at the earlier of the last post-baseline assessment or 336 hours after randomization. Subjects without any information after baseline (i.e., randomization) will be considered censored at 1 minute.

	Statistical Analysis Plan
	Sponsor: NOVARTIS
	Protocol number: CRLX030A3301

In case of missing time of in-hospital WHF or death or rehospitalisation for heart failure then 00:00 will be imputed.

According to the information from the endpoint adjudication committee, the following rules will be applied to determine if an endpoint reported in eCRF should be considered valid for the analysis or not:

Table 5.2-3: Rule for inclusion of events into the analysis

	Included in the analysis
WHF/death occurred within Day 5, reported in the dedicated page of the eCRF and confirmed by adjudication committee	YES
WHF/death occurred within Day 5, reported in the dedicated page of the eCRF and NOT confirmed by adjudication committee	NO
WHF/death occurred after Day 5 through Day 14 and reported in the dedicated page of the eCRF	YES
Readmission for heart failure reported in the dedicated page of the eCRF	YES

Censoring and time will be defined according to the following rule:

Table 5.2-4: Censoring and time rules

	Status	Time
At least one in hospital WHF/death/readmission for HF occurred and: Difference between date and time of first occurrence of WHF/death/readmission for HF and date and time of randomization +1 minute >336 hours	Censored	336h
Difference between date and time of first occurrence of WHF/death/readmission for HF and date and time of randomization +1 minute ≤336 hours	Event	Calculated difference
No in hospital WHF/death/readmission for HF occurred and: Difference between date and time of last assessment* and date and time of randomization +1 minute >336 hours	Censored	336h
Difference between date and time of last assessment* and date and time of randomization +1 minute ≤336 hours	Censored	Calculated difference

* Last assessment is the date and time of last available post-baseline physician assessment of in-hospital WHF

In case a patient is lost to follow-up, only the data until the last post-baseline in-hospital WHF assessment available will be considered in the analysis.

Treatment groups will be compared with a Gehan's generalized Wilcoxon test. The Kaplan-Meier estimates of the survival functions for each treatment group will be plotted. The Kaplan-

	Statistical Analysis Plan
	Sponsor: NOVARTIS Protocol number: CRLX030A3301

Meier estimates of the cumulative event rate will also be presented in tables by treatment group for each day and also by time interval (>0-5 days, >5-14 days).

Absolute frequencies and proportions of patients with event (as defined in the time to event analysis), overall (in-hospital WHF/all cause death/readmission) and by type of event (in-hospital WHF; all cause death; readmission), through Day 14 in each treatment group will also be provided (percentages based on population of analysis).

In addition, a description of all in-hospital WHF that occurred through Day 14 will be provided: absolute frequencies and proportions of patients with in-hospital WHF at each assessment time point will be presented overall and by the concomitant medication given (new, restarted or increased dose of medication), and/or by the need of mechanical/surgical intervention (yes/no) for the in-hospital WHF.

A summary of number and percentage of patients with or without WHF events through Day 5 (recorded on “Clinical worsening of heart failure” eCRF page for adjudicated events), and from Day 6 through Day 14 (recorded on “Heart failure details” eCRF page for events not to be adjudicated), will be provided by treatment.

Persistent signs or symptoms of HF/ non-improvement

Absolute frequencies and proportions of patients with persistent symptoms or signs of HF / not showing an improvement at any visit vs. baseline (persisting need of IV therapy for HF) in each treatment group will be provided, and also at each assessment time point (24 hours, 48 hours, Day 3, Day 4) through Day 5 and at discharge, together with standard errors, asymptotic (Wald) and exact (Clopper-Pearson) confidence limits. The rates in the two groups will be compared by means of Chi square test at each time point. In case of cell frequencies less than 5, Fisher’s Exact test will be used.

Patients with persistent symptoms or signs of HF / not showing an improvement versus baseline conditions at each assessment time point are those patients who take any IV therapy for HF at the assessment time point as reported in the eCRF sections “IV Loop Diuretic Medication for Heart Failure” and “IV Medications Other than Loop Diuretics”.

Improvement in signs or symptoms of HF

A time-to-event analysis through Day 14 will be performed. Hazard ratios of being a responder for each of the signs and symptoms variables (response is defined as ≥ 1 point improvement from baseline) will be estimated using a Cox regression model with treatment as a factor.

Treatment groups will be compared with a Gehan’s generalized Wilcoxon test. The Kaplan-Meier estimates of the cumulative event rate will also be presented by treatment group.

One or more point improvement will be defined as a reduction from baseline of at least one point in the specific sign/symptom according to the score defined in the table below.

Statistical Analysis Plan

Sponsor: NOVARTIS

Protocol number: CRLX030A3301

Table 5.2-5: Scores for the definition of improvement

	Categorical value	Numerical value
Dyspnea on exertion	None	0
	Mild	1
	Moderate	2
	Severe (including dyspnea at rest)	3
Orthopnea	None	0
	1 pillow (10cm)	1
	2 pillows (20cm)	2
	>30 degrees	3
Edema	0	0
	1+	1
	2+	2
	3+	3
Rales	No rales	0
	Rales <1/3	1
	Rales 1/3-2/3	2
	Rales >2/3	3
Jugular venous pulse (JVP)	<6cm	0
	6-10cm	1
	>10cm	2
Body weight increase	No	0
	Yes	1

The scores will be presented as both categorical and continuous (i.e., numerical values in Table 5.2-5) statistics. Change from baseline will be computed as the baseline value subtracted from the post baseline values. Cross tabulation of categorical values at baseline and at each assessment time point will be presented by treatment group.

Each sign or symptom of HF, collected in “Physician Assessment of Signs and Symptoms of Heart Failure” eCRF page, will be analysed separately. The event is defined as ≥ 1 point improvement from baseline. The time to being a responder will be computed as the number of hours from randomization to the date and time of the first assessment at which a ≥ 1 point improvement from baseline is detected plus 1 minute. Subjects without an event will be censored at the earlier of the last post-baseline assessment of signs and symptoms of HF or 336 hours (i.e., 14 days) after randomization. Subjects without any information after baseline (i.e., randomization) will be considered censored at 1 minute. In case of missing time of assessment of signs and symptoms of heart failure then 00:00 will be imputed. The analysis will be performed excluding subjects with the following signs and symptoms at baseline: ‘None’ for Dyspnea on exertion and Orthopnea; ‘0’ for Edema; ‘No rales’ for Rales; ‘<6 cm’ or ‘Not evaluable’ for Jugular venous pulse, ‘No’ for Body weight increase.

Table 5.2-6: Censoring and time rules

	Statistical Analysis Plan
	Sponsor: NOVARTIS
	Protocol number: CRLX030A3301

	Status	Time
At least one (≥ 1) point improvement occurred and:		
Difference between date and time of first occurrence improvement (i.e., date and time of physician assessment where improvement was assessed) and date and time of randomization +1 minute > 336 hours	Censored	336h
Difference between date and time of first occurrence improvement (i.e., date and time of physician assessment where improvement was assessed) and date and time of randomization +1 minute ≤ 336 hours	Event	Calculated difference
No improvement occurred and		
Difference between date and time of last available physician assessment and date and time of randomization +1 minute > 336 hours	Censored	336h
Difference between date and time of last available physician assessment and date and time of randomization +1 minute ≤ 336 hours	Censored	Calculated difference

Moreover, summary statistics for data about physician assessment of signs and symptoms of HF will be provided at each assessment time point by treatment group. Absolute and relative frequencies of patients reporting each sign/symptom will be provided. Percentages will be computed considering patients with non-missing information at each assessment time point and by each type of sign and symptom.

Renal deterioration

Renal deterioration will be assessed as the proportion of patients with an increase of ≥ 0.3 mg/dL from screening in serum creatinine levels. Absolute frequencies and proportions of patients with renal deterioration at each assessment time point in each treatment group will be provided, together with standard errors, asymptotic (Wald) and exact (Clopper-Pearson) confidence limits. Rate of renal deterioration in the two groups will be compared by means of Chi square test at each assessment time point. In case of cell frequencies less than 5, Fisher's Exact test will be used.

Index length of hospital stay

Index length of hospital stay (in hours) will be defined as the index hospitalization discharge date and time (obtained from the "Index hospitalization summary" eCRF page) minus the index hospitalization admission date and time plus 1 minute (obtained from the "hospitalization" eCRF page); it will be presented as elapsed hours.

Subjects still in the hospital at Day 30 will be censored at Day 30. Subjects who die during the initial hospitalization will be assigned the maximum length of stay (including those censored at Day 30) plus 24 hours.

Treatment groups will be compared using a Wilcoxon rank-sum test. Descriptive statistics by treatment group will be presented. Analysis will be done overall and by location for patients presented to Outpatient clinic or office / Ambulance or Emergency Medical Service / Emergency Department / Intensive Care Unit / Coronary or Cardiac Care Unit / Cardiology Ward / General Ward / Other, as recorded on the "Index heart failure hospitalization" eCRF page.

Statistical Analysis Plan

Sponsor: NOVARTIS

Protocol number: CRLX030A3301

Estimated duration (days) of stay in acute care unit (Coronary or cardiac critical care unit / General intensive care unit / Step down unit or telemetry unit / Cardiology department or cardiac ward / General ward), as recorded on the “Index hospitalization summary” eCRF page, will be summarized by treatment group.

Death through Day 30

